5.1.2. CAM2038 q4w (Once Monthly)

SC CAM2038 q4w has been investigated in one bridging clinical pharmacokinetic trial in healthy volunteers versus repeat dose CAM2038 q1w (i.e., at steady state), repeat dose SL BPN (i.e., at steady state), and single dose of IV BPN (Trial HS-13-487). The following conclusions can be drawn regarding the clinical properties of CAM2038 q4w:

- Extended BPN release over 4 weeks at target plasma concentrations
- 6- to 8-fold higher bioavailability versus SL BPN, comparable to CAM2038 q1w
- BPN plasma concentrations over 4 weeks comparable to CAM2038 q1w over one week, and to SL BPN over 24 hours at steady state (i.e., for approved 8 mg, 16 mg, or 24 mg doses), supporting dose selection for this Phase III trial
- Predicted $C_{ss,av}$ and $C_{ss,trough}$ values for CAM2038 q4w similar to CAM2038 q1w and SL BPN (i.e., for approved 8 mg, 16 mg, or 24 mg doses)
- Safety profile comparable to reference IV and SL BPN treatments
- Good local tolerability

The most commonly reported drug-related AEs after CAM2038 q1w and CAM2038 q4w administration were nausea (63% of subjects), dizziness (54% of subjects) and vomiting (39% of subjects). The local tolerability was good with 6 subjects experiencing 7 AEs that were assessed as related to CAM2038 q4w (injection site reactions, injection site pain, injection site induration and application site bruise). Two SAEs were reported by 2 subjects after treatment with 192 mg CAM2038 q4w. The first SAE was an event of withdrawal reaction and the second SAE was an event of dehydration due to nausea and vomiting. Both SAEs were assessed as related to CAM2038 q4w (withdrawal reaction was also assessed as related to the concomitant treatment with naltrexone) and the event of withdrawal reaction qualified for reporting as a suspected unexpected serious adverse reaction (SUSAR). There were no deaths or any other significant AEs and most of the AEs were mild and transient. Analysis of clinical chemistry, hematology and urinalysis parameters did not suggest any significant safety issues for CAM2038 q4w.

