Overall, features of CAM2038 q1w and q4w may increase patient compliance relative to daily SL BPN dosage forms, and may help prevent treatment noncompliance in higher-risk patients (i.e., those patients who take “drug holidays” from their BPN when they wish to abuse illicit opioids). In addition, CAM2038 q1w and q4w may provide significant potential for reducing risks of diversion, abuse, and accidental pediatric exposure, which continue to be important public health consequences of SL BPN therapy.

Therefore, the purpose of this trial is to demonstrate the efficacy and safety of CAM2038 (q1w and q4w) as an office-based therapy for initiation and continuation of opioid maintenance treatment with BPN in patients with opioid use disorder.

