9.2. Identity of Investigational Products

The following treatments will be used during the trial:

- CAM2038 q1w (BPN FC Injection depot for once weekly administration), 50 mg/mL: 8, 16, 24 and 32 mg (BPN base), 0.16, 0.32, 0.48 and 0.64 mL SC injection.

- CAM2038 q4w (BPN FC Injection depot for once monthly administration), 356 mg/mL: 64, 96, 128 and 160 mg (BPN base), 0.18, 0.27, 0.36 and 0.45 mL SC injection.
- CAM2038 placebo: 0.16, 0.32, 0.48 and 0.64 mL SC injection for once weekly or once monthly administration.
- SL BPN: 2 mg/0.5 mg or 8 mg/2 mg BPN/naloxone tablets.
- SL placebo: tablets matching 2 mg/0.5 mg and 8 mg/2 mg SL BPN doses.
- SL BPN film (test dose on Day 1): 4 mg/1 mg BPN/naloxone film.

Description of CAM2038 q1w, q4w, and placebo SC injection products:

CAM2038 q1w will be supplied as pre-filled syringe with safety device and plunger containing the following: BPN, soybean phosphatidylcholine, glycerol dioleate, and ethanol.

CAM2038 q4w will be supplied as pre-filled syringe with safety device and plunger containing the following: BPN, soybean phosphatidylcholine, glycerol dioleate, and N-Methyl-2-pyrrolidone.

Placebo SC injections will be supplied as matching for CAM2038 q1w or nearly matching (by volume and color) for CAM2038 q4w pre-filled syringes with safety devices and plungers containing the following: soybean phosphatidylcholine, glycerol dioleate, and ethanol. More information regarding the CAM2038 q1w, CAM2038 q4w and matching/near-matching CAM2038 placebo injections can be found in the Trial MOP.

Description of SL BPN and placebo tablets:

Subjects will be required to take daily SL BPN (BPN/naloxone) during the trial. These products will be supplied by the Sponsor or designee. Matching SL placebo tablets will be provided for each dosage strength. More information regarding the SL BPN and near-matching SL placebo products can be found in the Trial MOP.

All containers/packages/boxes of trial drug will be clearly labeled with trial-specific information meeting all the applicable regulatory/institutional requirements.

Description of SL BPN film (test dose):

All subjects will receive a 4 mg test dose of BPN/naloxone on Day 1. The test dose consists of 1 film of Suboxone[®] containing 4 mg BPN and 1 mg naloxone (Indivior UK Limited). Handling and storage of the product will be in accordance with the Suboxone Summary of Product Characteristics.

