12.3.2.5. Analysis of Exploratory Efficacy Endpoints

The exploratory efficacy endpoints will include RR during weeks on CAM2038 q1w (Phase 1) and during months on CAM2038 q4w (Phase 2). RR for Phase 1 and Phase 2 will be analyzed using chi square test. The percentages of negative urine samples in Phase 1 and Phase 2 will also be analyzed using chi square test. The 95% confidence intervals of the estimates will be presented using normal approximation.

Additionally, the following exploratory efficacy variables will be analyzed:

- Percent of subjects with evidence of no illicit opioid use by time point;
- Cumulative percentage of subjects with evidence of no illicit opioid use by time point;
- Percent of subjects with no self-reported illicit opioid use by time point
- Percent of subjects meeting criteria of stability at Week 13
- Changes from baseline in Desire to Use VAS, Need to Use VAS, COWS and SOWS over time.
- Percent of subjects without evidence of using other drugs of abuse by time point
- Supplemental BPN use
- Additional supplemental counseling
- Measures of morning need to use/desire to use
- Quantity of illicit opioid use

For the exploratory efficacy variables based on the percentages, the percentages, the differences of percentages (based on normal approximation) and 95% confidence intervals of the differences will be presented. Change from baseline variables will be analyzed via Analysis of Covariance (ANCOVA) model with treatment and baseline effects. Treatment effects and treatment differences will be estimated. The two-sided 95% confidence intervals of the between- and within-treatment differences will be presented.

Details of additional measures of efficacy and their analysis will be described prospectively, prior to final database lock and unblinding, in the SAP for this trial.

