10.2 ADVERSE EVENTS

Each AE and serious adverse event (SAE) term recorded on the CRFs will be mapped to a primary system organ class (SOC) and a preferred term using the MedDRA dictionary. The investigator will assess AE severity and relationship to the study treatment.

Columbia Suicide Severity Rating Scale (C-SSRS) will be summarized.

A treatment-emergent adverse event (TEAE) is defined as any AE with an onset date on or after date of randomization, or any ongoing event on the date of first dose that worsens in severity after date of randomization. Only TEAEs with an onset date prior to date of last dose + 30 days will be tabulated in

summary tables. For the purpose calculating treatment emergence and inclusion in summary tables, incomplete onset dates will be imputed as detailed in Appendix A.

TEAEs will be summarized by the number and percent of subjects in each primary SOC and preferred term. Patients will be counted only once for each primary SOC and each preferred term. Summary tables of TEAEs by primary SOC, preferred term and intensity will be provided. If a subject has more than one AE coded to the same preferred term, the subject will be counted only once for that preferred term by using the event with the highest intensity. Similarly, if a subject has more than one AE within a primary SOC category, the subject will be counted only once in that SOC category by using the event with the highest intensity. AEs by primary SOC, preferred term and relationship to study drug will be provided as well. If a subject has more than one AE coded to the same preferred term, the subject will be counted only once for that preferred term by using the most related event. Similarly, if a subject has more than one AE within a primary SOC category, the subject will be counted only once in that primary SOC category by using the most related event. In addition, SAEs by primary SOC and preferred term will be provided. Deaths and SAEs will be summarized similarly to AEs. All TEAE tables will also include the total number of events, counting multiple events per patient.

Injection related AEs, other (non-injection related) AEs as well as all AEs will be presented by treatment group and overall. Summaries of these AE subsets will be presented for the following categories:

- Study drug related
- Intensity
- Relationship to injection
- Possibly study drug related by intensity
- Reasonably injection related by intensity
- Serious

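### No adverse-event or exposure table is planned by phase, so event rates on the monthly depot are not reported for the subjects who received it

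*SAP*

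**What the plan says.** SAP 10.2 sets the tabulation: "TEAEs will be summarized by the number and percent of subjects in each primary SOC and preferred term". It adds "Patients will be counted only once for each primary SOC and each preferred term", and also "All TEAE tables will also include the total number of events, counting multiple events per patient". The window opens at randomization, and "Only TEAEs with an onset date prior to date of last dose + 30 days will be tabulated in" summary tables. Under SAP 5.1 the safety population is everyone with any dose. Exposure (SAP 10.1) is shown by treatment group. The one time slice for adverse events is the first week after randomization, which falls in the weekly phase. Appendix B Tables 14.3.1, 14.3.2 and 14.3.5.1 to 14.3.12 carry no split by phase or product.

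The two depots are different products. Protocol 9.2 describes q1w as 50 mg/mL with ethanol and q4w as 356 mg/mL, containing "BPN, soybean phosphatidylcholine, glycerol dioleate, and N-Methyl-2-pyrrolidone". SAP 9.1.1 places the q4w injections at Weeks 13, 17 and 21 only. On earlier experience, Protocol 5.1.2 states: "SC CAM2038 q4w has been investigated in one bridging clinical pharmacokinetic trial in healthy volunteers".

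Protocol 5.2 gives the trial's purpose as showing efficacy and safety of CAM2038 and names both q1w and q4w. Protocol 12.3.2.5 and SAP 9.3.1 to 9.3.4 analyse response rate and percent negative urines separately for Phase 1 and Phase 2.

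**The concern.** For most of the active arm's adverse-event output, a reader of the study report could not tell which depot an event followed. Two mechanisms are at work. First, subjects who leave before Week 13 never receive q4w but stay in the denominator, which lowers the apparent rate of any term that arises only on q4w. Second, a subject counts once per term over the whole window, so a term common to both phases mixes Phase 1 incidence into the Phase 2 comparison and pulls the contrast between arms toward equality.

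At stake is the first q4w safety evidence in patients that the protocol reports. The efficacy plan recognises that the two phases test different products; the adverse-event plan does not.

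**Working it through.** **Plan's own figures.** The SAP states no safety figure to reproduce. The only planned number used below is 190 subjects per arm (SAP 9.6). Its stated power of about 82% reproduces with that section's inputs (70% in both arms, margin 13.5 points): Φ(0.135 / √(2 × 0.7 × 0.3 / 190) − 1.96) = 0.819. Nothing below depends on that power.

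**Which safety output is resolved in time**

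| Output | Source | Time split |
|---|---|---|
| Response rate, percent negative urines | SAP 9.3.1 to 9.3.4 | Phase 1 and Phase 2 |
| Solicited injection-site findings | Tables 14.3.4.1 to 14.3.4.3 | By time point |
| Laboratory, ECG | SAP 10.3, 10.6 | By visit |
| Vital signs | Table 14.4.5 | By visit |
| Exposure | SAP 10.1, Table 14.3.1 | None |
| TEAEs, related TEAEs, SAEs, discontinuations | SAP 10.2, Tables 14.3.2 and 14.3.5 to 14.3.11 | None, apart from the first-week summary in SAP 10.2 |

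**Dilution by the denominator.** Let f be the share of the CAM2038 arm that receives the first q4w injection. The documents give no value, so f is assumed. Let r be the true rate, among q4w-treated subjects, of a term that arises only on q4w. The planned table shows r × f. The 5% summary in SAP 10.2 is reached only if r ≥ 5% / f.

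| f (assumed) | q4w-treated, of 190 | r = 10% appears as | r needed to reach 5% |
|---|---|---|---|
| 60% | 114 | 6.0% | 8.3% |
| 70% | 133 | 7.0% | 7.1% |
| 80% | 152 | 8.0% | 6.25% |
| 90% | 171 | 9.0% | 5.6% |
| 100% | 190 | 10.0% | 5.0% |

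**Masking by pooling phases.** Let a be the Phase 1 rate of a term and b its Phase 2 rate, with the phases independent and f equal in both arms. The share of subjects ever counted is a + (1 − a) × f × b. For illustration, take a = 5% in both arms, then b = 5% on control and 10% on CAM2038. The Phase 2 contrast is 5.0 points, ratio 2.0.

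- f = 100%: 0.05 + 0.95 × 0.05 = 9.75% against 0.05 + 0.95 × 0.10 = 14.5%; difference 4.75 points, ratio 1.49.
- f = 80%: 8.8% against 12.6%; difference 3.8 points, ratio 1.43.
- f = 60%: 7.85% against 10.7%; difference 2.85 points, ratio 1.36.

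**Events not seen.** With zero events, the one-sided 95% upper bound is 1 − 0.05^(1/n). On 190 subjects it is 1.6%. On the 114 who would have received q4w at f = 60% it is 2.6%. The pooled denominator would overstate how much a zero count excludes for q4w.

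**The case against.** The strongest reply is that the information is not lost. Onset dates are collected (Protocol 10.4.1.1). Listings of adverse events, SAEs, discontinuations and dosing are planned (Appendix B), and SAP 10.2 leaves room for further safety analyses as appropriate. Rare SAEs can be placed by date from the listings. The stated safety objective is the safety of CAM2038 as a regimen, which whole-trial tables by arm do answer, and SAP 10.0 treats formal safety comparisons as post hoc.

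That reply defeats several stronger readings a reader might infer:

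- That q4w safety cannot be separated from q1w. It can be; what is missing is a prespecified tabulation. Local, laboratory, ECG and vital-sign data are already by time point or visit.
- That a q1w event hides its recurrence on q4w. Total events are shown, and the intensity tables take the worst event. Neither is by phase, however.
- That tables stop at 24 weeks. The window runs to 30 days after the last dose.
- That the pooled rate is mostly q1w because a completer has at least 13 weekly injections (Day 1, Day 4, Weeks 2 to 12) and 3 monthly ones, 3/16 = 19%. Injection count is a poor measure for systemic events: a completer spends 12 of 24 treatment weeks on each product, and the Phase 2 conversion (16 to 64, 24 to 96, 32 to 128 mg) keeps the four-week dose equal.
- That the two earlier SAEs after q4w show a hazard at this trial's doses. Both followed 192 mg, above the 160 mg maximum here, in healthy volunteers, and one was also attributed to naltrexone.

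What remains standing against the reply: listings are not rates, and an unspecified further analysis is not a plan. Tabulating by study drug actually received (SAP 10.0) does not help either, because SAP 4.2 defines two treatment groups and Appendix B separates no products.

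**Conclusion.** The gap is real and limited to the planned adverse-event and exposure tables. No q4w rate for TEAEs, related TEAEs, SAEs or discontinuations will be reported on the subjects who received q4w. Its size depends on dropout before Week 13, which the documents do not give. At an assumed f of 60% to 90%, a q4w-only rate is understated by 10% to 40% in relative terms; at f = 100% it is not understated at all. Masking of a term common to both phases does not need dropout, but the ratio of 1.49 rests on illustrative rates and independent phases. No primary efficacy conclusion is affected.

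**What to change.** Before unblinding, amend SAP 10.1 and 10.2 and Tables 14.3.1, 14.3.2 and 14.3.5 to 14.3.11. Keep the pooled tables and add two summaries by arm:

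- Phase 1: first blinded dose to before the first Phase 2 injection.
- Phase 2: that injection (active or placebo) to the end of the TEAE window.

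In each, use the subjects dosed in that phase as denominator, count each term once per phase, and give events per subject-time. Flag events that follow a supplemental q1w injection.

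Label the Phase 2 comparison descriptive and footnote its limits:

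- It is made among subjects who stayed, so randomization does not fully protect it.
- Effects of the last q1w dose may carry over (Protocol 9.7 gives up to 2 weeks).
- Scheduled elicitation of adverse events is weekly in Phase 1 but monthly in Phase 2.
- Completely missing onset dates are set to randomization (SAP Appendix A) and so fall in Phase 1.
- The placebo contains ethanol and no N-methyl-2-pyrrolidone, so a vehicle effect is not isolated.

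The cost is additional tables from dates already collected, with no new data and no change to conduct. The main downside is that readers may over-interpret a comparison among stayers, which the label and footnotes are meant to prevent.

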- AEs which led to discontinuation of treatment
- SAEs which led to discontinuation of treatment
- AEs occurring in 5% or greater of any treatment group (by preferred term)

In the AE summary, preferred terms within each SOC will appear in alphabetical order.

Frequencies for deaths and hospitalizations will also be summarized by treatment group and overall.

To assess the AE profile during the first week of treatment (first week after the randomization), TEAEs that occur within the first week of treatment will be presented.

Other safety analyses will be performed as appropriate

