14.0 APPENDICES

14.1 APPENDIX A - IMPUTATION ALGORITHM FOR PARTIAL AND MISSING DATES

This section describes missing date imputation methods.

For Adverse Events

If onset date is completely missing, onset date is set to date of randomization.

If (year is present and month and day are missing) or (year and day are present and month is missing):

- If year = year of randomization, then set month and day to month and day of randomization
- If year < year of randomization, then set month and day to December 31.
- If year > year of randomization, then set month and day to January 1.

If month and year are present and day is missing:

- If year=year of randomization and
 - If month = month of randomization then set day to day of first dose
 - If month < month of first dose then set day to last day of month
 - If month > month of first dose then set day to first day of month
- If year < year of randomization then set day to last day of month
- If year > year of randomization then set day to first day of month

For all other cases, set onset date to date of randomization.

Concomitant Medications/Medical History

For start date

- If start date is completely missing, start date will not be imputed.
- If (year is present and month and day are missing) or (year and day are present and month is missing), set month and day to January 1.
- If year and month are present and day is missing, set day to 1st day of month.

For end date

- If end date is completely missing, end date will not be imputed.
- If (year is present and month and day are missing) or (year and day are present and month is missing), set month and day to December 31.
- If year and month are present and day is missing, set day to last day of the month.

Note: that if both start and end dates are missing then the medication will be classified as concomitant.

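### Appendix A date imputation can place later adverse events in the first-week TEAE summary, because SAP 10.2 gives that summary no dating rule of its own

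*SAP*

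**What the plan says.** SAP 10.2 states how partial onset dates are handled: "For the purpose calculating treatment emergence and inclusion in summary tables, incomplete onset dates will be imputed as detailed in Appendix A". The rule therefore has two stated uses, treatment emergence and entry into summary tables.

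Later in the same section the SAP adds a presentation for early events, introduced by "To assess the AE profile during the first week of treatment (first week after the randomization" and completed by "TEAEs that occur within the first week of treatment will be presented". It gives no dating rule, flag or exclusion for this presentation, and SAP Appendix B lists no table for it.

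SAP Appendix A (14.1) gives these rules for adverse events:

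- Wholly missing date: "If onset date is completely missing, onset date is set to date of randomization".
- Month missing: "If year = year of randomization, then set month and day to month and day of randomization".
- Day missing, same year, randomization month: "If month = month of randomization then set day to day of first dose".
- Day missing, same year, later month: "If month > month of first dose then set day to first day of month".
- Any case not listed goes to the randomization date.

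Under Protocol 7.1.2, randomization and the first blinded dose both take place on Day 1, so the first three rules and the residual rule all give Day 1.

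**The concern.** One imputation rule serves two questions whose errors run in opposite directions. For treatment emergence, the earliest plausible date is cautious, because no event is wrongly dropped as pre-treatment. For membership of a seven-day window, the same choice creates false positives: an event known only to belong to a given month or year is counted as an induction event.

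The first-week presentation is the only adverse-event summary aimed at induction, where the arms differ most in how treatment is delivered (depot injections against sublingual titration). Misplaced events would raise first-week counts in both arms and pull a ratio between arms towards 1. If retention or later event rates differed between arms, the additions could be unequal.

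**Working it through.** The plan states no figure on this point, so there is none to reproduce. The check applies Appendix A literally and then asks what share of the imputed events would be misplaced.

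**Inputs.** First week = Days 1-7 after randomization (SAP 10.2). Rules from SAP Appendix A. Observation to Day 175, the Week 25 day used in SAP 9.2.2. Assumption: onset is equally likely on each day under observation, with full follow-up. The number of incomplete dates is not given in the documents.

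**Step 1: worked dates.**

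| Randomized | Recorded onset | Imputed onset | Trial day |
|---|---|---|---|
| 10 March | March, day unknown | 10 March | 1 |
| 10 March | that year only | 10 March | 1 |
| 10 March | nothing | 10 March | 1 |
| 10 March | April, day unknown | 1 April | 23 |
| 29 March | April, day unknown | 1 April | 4 |

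The last row is a spill-over. When randomization falls in the last six days of a month, the first of the next month lies within Days 2-7, so a day-missing event from that next month also enters the first week.

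**Step 2: day missing, randomization month.** Take a 30-day month with randomization equally likely on day r = 1 to 30.

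- Possible onset days from r to day 30: sum of (31 − r) = 465.
- Of these, Days 1-7: 24 × 7 + (6 + 5 + 4 + 3 + 2 + 1) = 168 + 21 = 189.
- Truly first-week: 189/465 = 40.6%. Misplaced: 276/465 = 59.4%.

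With actual calendar months over a 366-day year the misplaced share is 59.9%. Taking all day-missing events imputed into Days 1-7, including the spill-over, it is 67.8%.

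**Step 3: month missing, randomization year.** Randomization equally likely on each day of a 366-day year.

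- Onset days inside the randomization year: 192 dates × 175 + (174 × 175)/2 = 33,600 + 15,225 = 48,825.
- Of these, Days 1-7: 360 × 7 + 21 = 2,541.
- Misplaced: 1 − 2,541/48,825 = 94.8%.

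**Step 4: date wholly missing.** Misplaced: 1 − 7/175 = 96.0%.

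**Step 5: front-loaded onset.** A constant rate is doubtful if events cluster at induction. If a share w of undated events truly starts in Week 1, the misplaced share is 1 − w:

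| w | Misplaced share of undated events |
|---|---|
| 4% (constant rate) | 96% |
| 20% | 80% |
| 40% | 60% |
| 60% | 40% |

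These are shares of the incompletely dated events, not of the first-week table.

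**The case against.** The strongest reply is that the SAP does not say the first-week presentation uses imputed dates. The imputation sentence directly follows the cut-off at 30 days after the last dose, so inclusion in summary tables may mean only that cut-off. This reading is possible. It does not remove the problem, because it leaves no rule at all for partially dated events in the first-week presentation. The point is therefore what follows if the SAP is applied as written; the SAP does not state it outright.

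Second, incomplete dates may be rare. Onset date is a required item (Protocol 10.4.1.1), adverse events are elicited at every clinic visit (Protocol Table 3), and entries are checked against source (Protocol 11.1). This stands, and it limits the practical importance.

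Third, SAP 10.0 pre-specifies no safety outcome and makes any formal safety comparison post hoc. The rule is also the same in both arms, and similar additions to both leave a difference in counts largely unchanged. This stands too.

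A reader might infer three stronger things that the documents do not support:

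- That induction safety is seen nowhere else. ECG and vital signs are taken around dosing on Day 1 and again on Day 8, COWS is repeated on Day 2, and injection-site findings are collected from Day 1 and tabulated by time point.
- That the table would sweep in undated events from the whole trial. An event with a known later month goes to the first of that month; whole-trial capture needs the month itself to be missing in the randomization year, or no usable date.
- That the first-week results would be materially wrong. Without the number of incomplete dates, no effect on the table can be shown.

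**Conclusion.** The point holds as a minor defect of specification. Followed as written, SAP 10.2 and Appendix A can count later events as first-week events. Under a constant event rate over 175 days with full follow-up, about 60% of day-missing events in the randomization month and about 95% of month-missing or undated events would be misplaced. For undated events the share falls to between 80% and 40% if 20% to 60% of them truly start in Week 1. The effect on the summary itself is unknown and may be small. No efficacy conclusion and no planned safety test is affected.

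**What to change.** Keep Appendix A unchanged for treatment emergence. Add to SAP 10.2 a rule along these lines: in the first-week summary, the main row counts TEAEs whose recorded date parts place onset in Days 1-7; TEAEs placed in that window only by Appendix A appear in a separate row; totals are given with and without that row. Add the table to Appendix B.

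Appendix A gives a post-randomization event the earliest date its recorded parts allow, so the separate row holds every incompletely dated TEAE that could have started in the first week. The two totals then bracket the true count, and no event is lost.

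The cost is one sentence, one table entry and one extra row. The downside is that some true first-week events with partial dates appear only in the separate row and the combined total, which is why both totals should be shown. The rule should be set before unblinding; afterwards it would be a post hoc choice.
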